6.4.3.1 Primary Analyses

We will calculate the NRS scores between the two treatment arms as overall procedure pain collected at the time of dressing application. An independent group t-test will be used to assess whether the NRS scores differ between the groups. Descriptive data will be calculated for all variables. The characteristics of patients in the two groups will be compared in order to confirm adequacy of randomization. If there is unequal distribution of background variables with p values of 0.15 or less, we will include them in a multivariable analysis of the outcomes.

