6.3 Study Procedures

- The RAs and attending physicians will identify eligible patients. To participate, patients must have capacity to provide informed consent.
- The healthcare provider and the RA will describe the study to eligible patients and obtain patient consent.
- The RA will weigh patient, obtain a baseline NRS pain score and initial vital sign information.
- The RA will have the nurse remove the next study packet from the PYXIS, which will be either 4 mL vial containing either fentanyl 50mcg/mL or sterile water. The contents will be concealed by the research pharmacist.
- Patients will receive the blinded study medication either 2 mcg/kg of fentanyl or 0.04 mL/kg of sterile water (max 4mL) weight based and rounded to the nearest 10kg (excluding patients > 100kg to prevent excessive opioid dosing) via an atomizer syringe (half of total volume in each nostril) 15 minutes prior to local infiltration
- The RA will prompt the treating provider 15 minutes after local infiltration to ensure prompt treatment during an optimal systemic and local analgesic window. If the I&D has not been initiated within 30 minutes of INF administration the patient will not be included in the analyses due to concern for considerable tapering of INF analgesia (accounted for in sample size calculation).
- At 15 minute intervals following the intranasal medication administration, the RA will obtain vital signs (including SaO₂ by pulse oximeter), and record incidence of side effects and adverse events.
- The RA will record all medications administered in the ED and the time of their administration from the chart and the treating attending physician.

- RAs will record the time of each pertinent procedural step: Initial NRS collection time, location of abscess, size of abscess (cm), complexity of procedure (simple: requires minimal blunt instrumentation, moderate: requires more than minimal blunt instrumentation, complex: requires more than moderate instrumentation), use of packing (yes/no), study medication administration time, local infiltration time, incision/instrumentation/packing /irrigation time, dressing application time and discharge time.

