6.4.2 Sample Size Considerations

A sample size of 49 patients will support the primary outcome, based on the observed SD of 3.2, if the between group difference is no less than 2.8. This was calculated based on the following parameters: alpha = 0.05 and power = 0.8. Although smaller differences may be clinically relevant, a between-group difference of 2.8 is generally regarded as a robust difference.

We used nQuery Advisor version 7.0 (Los Angeles, CA) to calculate the sample size.

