6.4.3.2 Secondary Objectives Analyses

A similar analysis to the primary outcome analysis will be performed for NRS pain immediately after local analgesic infiltration, for NRS pain score after abscess incision and (instrumentation

and/or packing if completed) between the two treatment arms. We will calculate the difference in the proportion of patients in each group who are satisfied with treatment based upon a categorical patient-centered question answered as "Satisfied, Neutral, Not Satisfied." A chi-square test will be used to compare the proportions of patients who are satisfied with treatment. The same analyses will be done to determine provider perception of efficacy of analgesia of study medications compared to usual care.

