6.4.3.3 Safety

Vital sign data and side-effects, including adverse events, will be obtained and recorded at 15 minute intervals after medication administration to ensure patient safety. Chi-square tests will be used to assess whether the proportion of patients with one or more side effects differs between treatment groups. The individual side effects will be described in tables. If there are marked differences between the distributions of background characteristics, a multi-variable regression will be performed to control for possible confounding.

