6.4.3.4 Analysis of Subject Characteristics

- Background characteristics: Age, sex, race/ethnicity, initial pain intensity, nausea and vomiting before administration of analgesics. Means and standard deviations, medians and interquartile ranges, and proportions will be used to describe the sample as appropriate.

7 - Trial Administration

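### Covariates for the adjusted analysis are chosen by baseline significance tests (p ≤ 0.15), when baseline NRS could be fixed in advance; the adjusted result has no stated rank against the t-test

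*Combined protocol and SAP*

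**What the plan says.** For the primary outcome, section 6.4.3.1 states: "An independent group t-test will be used to assess whether the NRS scores differ between the groups". It then has baseline characteristics compared between arms as a check on the randomisation and continues, in the event of "unequal distribution of background variables with p values of 0.15 or less, we will include them in a multivariable analysis of the outcomes".

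The candidates appear to be those in section 6.4.3.4: "Background characteristics: Age, sex, race/ethnicity, initial pain intensity, nausea and vomiting before administration of analgesics". That is five or six variables, depending on whether nausea and vomiting count as one or two. Section 6.3 also has abscess size, location and complexity recorded, and the plan does not say whether these count as background variables.

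Baseline pain is measured before study drug (section 6.3): "The RA will weigh patient, obtain a baseline NRS pain score and initial vital sign information". Nothing in the document makes it a fixed covariate.

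Section 6.4.3.2 extends the approach: "A similar analysis to the primary outcome analysis will be performed for NRS pain immediately after local analgesic infiltration", and likewise for the score after incision and drainage. Section 6.4.3.3 uses a different trigger with no threshold: "If there are marked differences between the distributions of background characteristics, a multi-variable regression will be performed to control for possible confounding".

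**The concern.** Under valid randomisation, any baseline difference between arms is due to chance. A test of that difference says nothing about whether the variable predicts procedure pain, which is what decides whether adjusting for it gains precision. A rule based on the test can bring in irrelevant variables and leave out the obvious candidate, initial pain on the same 0–10 scale.

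Two things are at stake. If baseline pain predicts procedure pain, the plan gives up power for which it already has the data. The rule also produces a second, data-selected estimate that can disagree with the t-test, and the plan does not say whether that estimate is primary, supportive or a replacement.

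**Working it through.** **Inputs.** From section 6.4.2: difference 2.8, SD 3.2, alpha 0.05, power 0.8, 49 patients. Assumed because not stated: two-sided test, 1:1 allocation, 49 as the total, and a loss of about 10%. Section 6.3 says that exclusions for late procedures are allowed for in the sample size but gives no rate. The correlation r is not in the documents and is varied.

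**Reproducing the 49.** Normal approximation: n per arm = 2(1.960 + 0.842)² × (3.2/2.8)² = 20.5, so 21. Exact noncentral-t power is 0.790 with 21 per arm and 0.809 with 22, so 22 per arm (44 in total) are needed. With 10% loss, 44/0.9 = 48.9, so 49. This matches the plan.

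**t-test at 22 per arm.** Noncentrality = 2.8 / (3.2 × √(2/22)) = 2.90 on 42 df; power 0.809.

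**Fixed ANCOVA on baseline NRS.** Residual SD = 3.2 × √(1 − r²), with 41 df:
- r = 0.3: SD 3.05, noncentrality 3.04, power 0.844. The difference detectable with 80% power falls from 2.77 to 2.64.
- r = 0.5: SD 2.77, noncentrality 3.35, power 0.905. The detectable difference falls to 2.40.

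**Simulation of the rule.** 22 per arm; five or six independent normal baseline variables, of which only baseline NRS is related to the outcome; 12,000 trials per scenario at a true difference of 2.8. Chance imbalance in the covariate is included, so ANCOVA comes out slightly below the formula.

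| Assumed r | t-test (exact) | p ≤ 0.15 rule (5 / 6 variables) | Fixed ANCOVA (5 / 6 variables) |
|---|---|---|---|
| 0 | 0.81 | 0.79 / 0.78 | 0.80 / 0.80 |
| 0.1 | 0.81 | 0.78 / 0.77 | 0.81 / 0.80 |
| 0.3 | 0.81 | 0.80 / 0.78 | 0.84 / 0.84 |
| 0.5 | 0.81 | 0.81 / 0.80 | 0.90 / 0.90 |

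Up to r = 0.5 the rule recovers none of the available gain. At r = 0.7 (8,000 trials, five variables) the figures are 0.81 for the t-test, 0.83 for the rule and 0.97 for ANCOVA.

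**How often the rule acts.** Baseline NRS is selected in 14.6–15.3% of trials, as a 0.15 threshold implies. At least one variable is selected with probability 1 − 0.85⁵ = 0.556 for five independent variables, or 1 − 0.85⁶ = 0.623 for six. With nausea at 10% and vomiting at 5% nested within it (both rates assumed), the probability is 0.48 using Fisher tests for the binary variables and 0.64 using Pearson chi-square.

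**Disagreement.** At a true difference of 2.8, the t-test and the rule's model fall on opposite sides of 0.05 in 4.5–8.3% of trials. Under no effect this is rarer, 1.4–3.0%.

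**Type I error** (16,000 trials per scenario). The rule's model alone gives 3.9–5.1% with five variables at r up to 0.5 or six at r up to 0.3. It is lower when r is higher (3.4% with six variables at r = 0.5; 2.8% with five at r = 0.7). Claiming success if either result were significant would give about 6%.

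**The case against.** The strongest reply is that the rank is implied. The t-test is the only test named under the primary-analysis heading, the sample size fits an unadjusted comparison of two means, and the multivariable model is conditional. That is the natural reading, and the t-test is taken as primary here. It still leaves unsaid what the adjusted model is for and what happens if it disagrees, although by chance alone such a model would be fitted in roughly half of trials or more.

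Second, the efficiency gain depends on an unknown correlation. The baseline score is pain before any procedure, whereas the outcome is pain provoked by infiltration and incision, so a high r cannot be presumed. This stands: the gain is 1 to 2 points at r = 0.2 and becomes material only from about 0.3. The trade is nevertheless lopsided, with about 1 point lost at worst against about 9 gained at r = 0.5.

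Third, error inflation is slight. This also stands. The rule's model errs on the conservative side, and the 6% figure needs an either-result claim that the plan does not make.

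Fourth, adjusting after a visible imbalance does protect against that imbalance. Under no effect at r = 0.5, among trials where baseline NRS is imbalanced enough to be selected, the t-test rejects in 12.7% and the rule's model in 4.7%. A fixed ANCOVA gives the same protection (4.6%) without a selection step.

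Finally, section 6.4.3.2 might carry over only the t-test. But the rule in 6.4.3.1 refers to outcomes in the plural, which supports the wider reading.

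**Conclusion.** The concern holds. The primary test is neither invalid nor, on the plan's own inputs, underpowered: power is 0.81 at 22 per arm, and 0.85 if all 49 are analysed. What is lost is precision and a single clear answer. Fixing baseline NRS in advance would raise power by about 3 points at r = 0.3 and 9 at r = 0.5, while the p ≤ 0.15 rule delivers none of this over that range. A second result would be triggered by chance in about 56–62% of trials if the variables are independent (48–64% under the sparse-data assumptions). It would conflict with the t-test in about 5–8% of trials if the planned difference is real.

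These figures rest on the assumed 10% loss, two-sided testing, 1:1 allocation, normal and independent baseline variables in the simulation, and the assumed values of r. The objection to choosing covariates by imbalance p-values does not depend on r; the size of the efficiency gain does. This should be corrected, but it does not threaten the validity of the trial.

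**What to change.** - **6.4.3.1:** make the primary analysis one pre-specified linear model of the NRS at dressing on treatment arm and baseline NRS. Delete the p ≤ 0.15 rule and the baseline significance tests, and present baseline characteristics descriptively. Keep the unadjusted t-test as a labelled sensitivity analysis.
- **6.4.3.2:** use the same model for the NRS after infiltration and after incision and drainage.
- **6.4.3.3:** replace the undefined trigger with covariates fixed in advance, or with no adjustment.
- **Minimum alternative, if the t-test stays primary:** say that it is primary, and name one supportive model with baseline NRS as its fixed covariate.

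The change is to wording only, since baseline NRS is already collected. The price is one degree of freedom and at most about 1 point of power (0.81 to 0.80) if baseline pain turns out to be unrelated to procedure pain.

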6.4.3.2 Secondary Objectives Analyses

A similar analysis to the primary outcome analysis will be performed for NRS pain immediately after local analgesic infiltration, for NRS pain score after abscess incision and (instrumentation

and/or packing if completed) between the two treatment arms. We will calculate the difference in the proportion of patients in each group who are satisfied with treatment based upon a categorical patient-centered question answered as "Satisfied, Neutral, Not Satisfied." A chi-square test will be used to compare the proportions of patients who are satisfied with treatment. The same analyses will be done to determine provider perception of efficacy of analgesia of study medications compared to usual care.

6.4.3.3 Safety

Vital sign data and side-effects, including adverse events, will be obtained and recorded at 15 minute intervals after medication administration to ensure patient safety. Chi-square tests will be used to assess whether the proportion of patients with one or more side effects differs between treatment groups. The individual side effects will be described in tables. If there are marked differences between the distributions of background characteristics, a multi-variable regression will be performed to control for possible confounding.

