In a randomized study, 47 pediatric patients presenting for long-bone fractures given 1mcg/kg of 50mcg/mL of INF vs 0.2mg/kg of 10mg/mL of intramuscular morphine (IMM) demonstrated fewer side effects with INF than IMM ($p<0.001$). This study also showed no difference in reduction in pain scores and no serious adverse events. One patient in the INF group required rescue analgesia.[22]

When comparing INF (1.4mcg/kg equivalent to 1mcg/kg calculated at 71% bioavailability) to intravenous morphine (0.1mg/kg) in 67 children < 18 years of age presenting to the emergency department for long bone fractures, VAS pain scores at 30 minutes decreased from 67 to 33 in the morphine group and 68 to 37 in the INF group (time=30 min difference 95% CI -4(-16 to 8)). Neither group had any cases of respiratory depression, hypotension, or decreased level of consciousness. Mean INF dose was 1.7mcg/kg due to additional doses of 15mcg, given as necessary. In the INF group 3 patients reported "bad taste" and one had an episode of vomiting 20 minutes after intervention. One patient in each group required additional doses of analgesia. [17]

In a study of 189 pediatric patients (3 to 15 years old) presenting for long bone fractures treated with 1.5mcg/kg of standard (50mcg/mL) vs high concentration (300mcg/mL) INF, both arms had substantial reduction in pain scores. Of these patients, 42(43%) in the standard concentration group required rescue medication compared with 25(28%) in the high concentration group.[17]

Fentanyl in the emergency department

The brief duration of action, potency and ease of administration, make fentanyl an optimal choice of analgesia in the emergency department. Despite this, fentanyl is used merely 10% as often as hydromorphone despite its favorable safety profile. [23]

A study by Imamoglu et al. looking at 115 adult patients receiving INF vs IV fentanyl (n=115) for renal colic, showed effective analgesia by both regimen at 15 and 30 min with rescue pain medication requirements of 55% in the IN group and 37% in the IV group (n=0.058). Adverse events occurred in 22% of patients in the IV group and only 9% in the IN group. None of these were serious.[24]

In a retrospective study of 841 patients looking at fentanyl for pre-procedural analgesia: 6 patients (0.7%) had mild side effects: nausea (1), vomiting (2), urticaria (1) and pruritis (2). Nine (1.1%) had more serious side effects including: respiratory depression (6), hypotension (3), both

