4.3 Secondary Objectives

- A) To compare pain scores immediately after local analgesic infiltration and after abscess incision, instrumentation and packing
- B) To compare patient satisfaction with treatment and provider perception of study medication efficacy compared to usual care
- C) To compare side effect profiles and adverse events associated with the administration of INF and placebo.

5 - Study Design

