6.1.3 Method of Assignment/Randomization

Randomization will occur in blocks of four based on a random number generator.

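### The safety comparison needs a difference in proportions with a confidence interval: an unnamed chi-square test on few events can give a variant-dependent verdict and cannot rule out a relevant excess

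*Combined protocol and SAP*

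**What the plan says.** Comparing safety is a stated secondary objective. Section 4.3, item C, reads: "To compare side effect profiles and adverse events associated with the administration of INF and placebo". For the analysis, section 6.4.3.3 says: "Chi-square tests will be used to assess whether the proportion of patients with one or more side effects differs between treatment groups". It names no variant (uncorrected or Yates-corrected), no exact test for small counts and no interval. It adds tables of the individual side effects, and a regression if background characteristics differ markedly.

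Section 6.2.1 lists the between-arm difference in the share of patients with any side effect as a secondary outcome, so an effect measure is named. Section 6.4.3.2 says that the difference will be calculated for patient satisfaction; 6.4.3.3 has no matching sentence for safety. No section plans a confidence interval for the safety difference.

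The sample size rests on pain alone (6.4.2): "A sample size of 49 patients will support the primary outcome, based on the observed SD of 3.2". No side-effect rate is assumed for either arm. Section 2.1 offers two intranasal figures. In an adult renal colic study, "Adverse events occurred in 22% of patients in the IV group and only 9% in the IN group". In a 24-patient cross-over study, 4 patients had nasal stinging.

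**The concern.** About 49 patients and event rates near those cited would produce only a handful of patients with a side effect. Three things follow.

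- The usual condition for the chi-square approximation, all expected counts at least 5, would rarely be met at those rates.
- With so few events, the uncorrected and corrected tests can fall on opposite sides of 0.05. The plan does not choose between them, so the choice is left to a software default or to an analyst who has seen the data.
- Power is low for modest excesses. A p-value above 0.05 would be weak evidence, and without an interval the reader cannot see how weak.

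What is at stake is how objective C can be read. The primary pain comparison is not affected.

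**Working it through.** **Inputs.** From 6.4.2: SD 3.2, difference 2.8, "alpha = 0.05 and power = 0.8" (two-sided assumed), total 49. From 6.1.3: blocks of four and two arms, so 1:1 is assumed. From 2.1: 9% and 4/24 = 16.7%. All placebo rates, and the 30% and 40% INF rates, are assumptions.

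**Reproducing 49.** The normal formula 2(z₀.₉₇₅ + z₀.₈)²σ²/δ² = 2 × (1.960 + 0.842)² × 3.2²/2.8² gives 20.5, so 21 per arm. The t-test version gives 21.5, so 22 per arm and 44 in total. Then 44/0.90 = 48.9, so 49. The 10% allowance is inferred: section 6.3 says that exclusions were allowed for but gives no rate. Reading 49 as per arm would give about 99% power, so 49 is taken as the total, with 24 INF and 25 placebo.

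**Expected counts.** With K patients having an event, the smaller expected event count is K × 24/49. It reaches 5 only if K ≥ 5 × 49/24 = 10.2, that is, 11 patients. At 9% in both arms, 49 × 0.09 = 4.4 patients are expected.

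**Exact enumeration.** For each pair of rates, sum Bin(a; 24, p₁) × Bin(b; 25, p₂) over all tables (a, b) that meet the stated condition.

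| INF vs placebo rate | All expected counts ≥ 5 | P(p<0.05), uncorrected / Yates | The two disagree at 0.05 |
|---|---|---|---|
| 9% vs 2% | <0.01% | 10.5% / 1.2% | 9% |
| 9% vs 9% (null) | 0.4% | 4.5% / 0.5% | 4% |
| 16.7% vs 5% | 1.2% | 25% / 9% | 15% |
| 16.7% vs 9% | 4.1% | 12% / 4% | 7% |
| 30% vs 10% | 37% | 42% / 29% | 13% |
| 40% vs 20% | 91% | 34% / 22% | 12% |

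**False positives.** With equal rates of 5, 9, 15, 20 and 30%, the uncorrected test rejects in 1.9, 4.5, 5.4, 5.2 and 5.1% of trials. There is no material inflation.

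**One table, three verdicts (4/24 vs 0/25).**
- Uncorrected: 49 × (4×25 − 20×0)² / (24×25×4×45) = 490,000/108,000 = 4.54, p=0.033.
- Yates: 49 × (100 − 24.5)² / 108,000 = 2.59, p=0.108.
- Fisher: C(24,4)/C(49,4) = 10,626/211,876 = 0.0502. The opposite extreme, 12,650/211,876, is more probable and is not added, so p=0.050, just above the limit.

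Similarly, 5/24 vs 0/25 gives 0.016, 0.053 and 0.022.

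**What a non-significant result leaves open (2/24 vs 1/25).** The uncorrected p-value is 0.53. The Wilson limits are 2.3% to 25.8% for 2/24 and 0.7% to 19.5% for 1/25, and the difference is 8.3 − 4.0 = 4.3 points. Newcombe's limits are:
- lower: 4.3 − √[(8.3 − 2.3)² + (19.5 − 4.0)²] = −12 points;
- upper: 4.3 + √[(25.8 − 8.3)² + (4.0 − 0.7)²] = +22 points.

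**Zero events.** The exact two-sided 95% upper limit for 0 of 24 is 1 − 0.025^(1/24) = 14%.

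**The case against.** The case for leaving the plan alone has four parts.

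- **An effect measure is already there.** Section 6.2.1 names the difference in proportions, 6.4.3.1 promises descriptive data for all variables, and 6.4.3.3 adds tables. This stands: a reader who infers that the plan offers nothing but a p-value would be wrong. What is missing is the interval and the name of the test.
- **The event rate is borrowed.** The 9% is an adverse-event rate in renal colic, whereas the planned endpoint counts any side effect. The documents give no rate for that composite, and nasal stinging alone affected 4 of 24. This also stands. A reader might infer that the expected-count condition will almost never hold, but that is so only at the cited rates; the table shows it met in 37% and 91% of trials at higher ones.
- **The uncorrected test keeps its size.** Correct, so an inflated false-positive rate should not be inferred. That does not settle which test will be run.
- **Low safety power is normal in a trial sized on pain, and no test cures it.** Correct. But that is the reason to show an interval.

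A reader might also infer that a null result is nearly certain even if INF clearly raises side effects. That is not shown: at 16.7% versus 0% the uncorrected test has about 59% power. Nor do the documents say that p>0.05 would be reported as absence of a difference.

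**Conclusion.** The point holds as a low-cost improvement to a secondary objective. Section 6.4.3.3 relies on a chi-square test of unstated form with no interval, in a sample sized for pain.

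- At the cited intranasal rates, with placebo assumed at 2% to 9%, all expected counts reach 5 in about 4% of trials or fewer.
- The uncorrected and Yates tests disagree at 0.05 in 9% of trials at 9% versus 2%, and in 15% at 16.7% versus 5%.
- Power for modest excesses runs from 10.5% (uncorrected) or 1.2% (Yates) at 9% versus 2% to 42% or 29% at 30% versus 10%.
- A non-significant 2/24 versus 1/25 remains compatible with an excess of 22 points.

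These figures assume that 49 is the total, that allocation is 1:1, that all patients count for safety, and the placebo rates shown. If the 30-minute exclusion in 6.3 also applies to safety, the denominators would be smaller: about 22 per arm under the inferred 10%.

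**What to change.** Reword 6.4.3.3 as follows.

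- Make the main safety result the difference, INF minus placebo, in the proportion of patients with any side effect, with a 95% confidence interval. Choose either a score-based or a Newcombe interval in advance.
- If a p-value is also wanted, name one test before unblinding, for example Fisher's exact test. State that the interval leads, since the two can differ at the margin: for 4/24 versus 0/25 Newcombe's interval runs from just above 0 to +36 points while Fisher's p is 0.0502.
- State that conclusions come from the interval and that p>0.05 will not be read as no difference.
- For each adverse event with no cases, give the exact upper confidence limit in each arm.
- State the safety denominator, and reconcile the side-effect window: 6.2.1 has both 60 minutes after the procedure and 120 minutes after dosing, and 6.4.3 has 120 minutes.

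The analysis changes cost wording only, with no new data or patients. The one drawback is that a wide interval looks less reassuring than a p-value alone.

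### Section 6.4.3.3 adds an adjusted side-effect analysis when baseline differences look marked: an undefined, data-driven trigger, too few likely events for a multi-covariate model, and no rule on which result leads

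*Combined protocol and SAP*

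**What the plan says.** Comparing side effects between arms is secondary objective C (section 4.3). For this, 6.4.3.3 sets a chi-square test on the proportion of patients with at least one side effect, without any condition, and tables of the individual effects. It then adds: "If there are marked differences between the distributions of background characteristics, a multi-variable regression will be performed to control for possible confounding". It does not define *marked*, name the model, list or limit the covariates, say which result leads, or say what happens if the model cannot be fitted.

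The primary analysis section, 6.4.3.1, has a different trigger: "If there is unequal distribution of background variables with p values of 0.15 or less, we will include them in a multivariable analysis". The sentence goes on to speak of outcomes in the plural, so it is unclear whether it also governs safety. Section 6.4.3.4 gives the candidate list: "Background characteristics: Age, sex, race/ethnicity, initial pain intensity, nausea and vomiting before administration of analgesics".

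The sample was sized on pain scores alone (6.4.2): "A sample size of 49 patients will support the primary outcome, based on the observed SD of 3.2". No side-effect rate is projected for either arm.

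**The concern.** Patients are allocated at random, so baseline differences between arms are chance differences. Choosing covariates because they happen to look imbalanced is not a sound way to deal with confounding; covariates should be chosen in advance because they predict the outcome. Under the present wording, someone who has seen the data decides whether an adjusted safety result exists and what goes into it. The two triggers do not match, and the plan has no answer if the adjusted and chi-square results point in different directions.

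The second difficulty is sparse data. A trial of 49 patients sized on a pain score may have only a few patients with side effects, and a logistic model with several covariates needs more. At stake is how clearly the main between-arm safety statement of an opioid trial can be read. The primary result is not affected.

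**Working it through.** **1. The plan's sample size.** Inputs from 6.4.2: SD 3.2, difference 2.8, "alpha = 0.05 and power = 0.8"; two-sided testing and 1:1 allocation are assumed.

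- Normal formula, per arm: 2 × (1.960 + 0.842)² × (3.2/2.8)² = 2 × 7.85 × 1.306 = 20.5, so 21 (42 in total).
- The t-test calculation gives 21.5, so 22 per arm (44 in total).
- 44/0.90 = 48.9, so 49 with a 10% allowance. Section 6.3 says that late procedures were allowed for but gives no rate, so the 10% is an assumption.
- Read as 49 per arm, power would be 99%. So 49 is taken as the total, about 25 and 24 per arm, and is not called wrong.

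**2. How often chance alone fires a trigger.** Six characteristics (6.4.3.4), treated as independent:

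- p ≤ 0.15: 1 − 0.85⁶ = 62%. With five variables, 1 − 0.85⁵ = 56%. Simulated trials give 62–64%, or 50–54% if Fisher's exact test is used for the binary items.
- p ≤ 0.05, a threshold assumed here: 1 − 0.95⁶ = 26%; with Fisher's test, 18–22%.

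**3. Expected patients with an event, and failed fits.** The rates are assumptions. The 9% and 22% come from the renal-colic study in section 2.1: "Adverse events occurred in 22% of patients in the IV group and only 9% in the IN group". The 2% stands for the retrospective fentanyl series there (0.7% + 1.1% = 1.8%). No placebo rate is given.

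The chance that at least one arm has no events is 1 − [1 − (1 − p₁)²⁵] × [1 − (1 − p₀)²⁴]. For 9% vs 2% this is 1 − (1 − 0.095)(1 − 0.616) = 65%.

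The two middle columns come from simulated trials of 49 patients in which the 0.15 rule fired. They assume covariates unrelated to outcome, baseline nausea 10% and vomiting 5%. Ranges span repeat simulations, which differ in covariate details and in how a failed fit was detected.

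| Fentanyl vs placebo | Expected patients with an event | Any coefficient non-estimable | Treatment coefficient non-estimable | No events in at least one arm (formula) |
|---|---|---|---|---|
| 9% vs 2% | 25×0.09 + 24×0.02 = 2.7 | 79–85% | 66–67% | 65% |
| 9% vs 9% | 49×0.09 = 4.4 | 48–59% | 20–21% | 19% |
| 22% vs 9% | 25×0.22 + 24×0.09 = 7.7 | 36–41% | about 10% | 11% |
| 22% vs 22% | 49×0.22 = 10.8 | 21–26% | under 1% | 0.5% |

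The last two columns nearly coincide. The treatment coefficient is lost when an arm has no events; the remaining failures sit in the covariates.

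**4. Dependence on covariates and event rate.** With treatment plus five covariate terms there are six parameters, so 2.7 to 10.8 events give 0.45 to 1.8 events per parameter. Without conditioning on a trigger, the share of fits with no finite solution rises from 28% with one covariate to 69% with five terms at 9% vs 9%, and from 13% to 44% at 22% vs 9%. At 40% vs 20% (about 15 events) it is 0.4% and 12%.

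**5. The chi-square test.** The smallest expected cell is (total events) × 24/49. With 10 events it is 4.9 and with 11 it is 5.4, so it falls below 5 whenever there are 10 or fewer. That happens in about 100% of trials at 9% vs 2% and 87% at 22% vs 9%.

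**The case against.** The strongest reply is that the regression is only an addition. The chi-square test is unconditional, so an unadjusted comparison is reported whatever the baseline shows. A reader might infer that the plan switches to the regression, or lets it replace the simple comparison. The text does not say so. What remains is that no order of precedence is given.

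A reader might also infer from the high failure rates that adjustment will often leave no usable treatment estimate. That does not follow. Most of those failures concern a covariate, such as a rare baseline symptom with no events, while the treatment odds ratio stays finite. Where the treatment coefficient does fail, one arm nearly always has no events, and the unadjusted odds ratio is undefined as well. Only 9% vs 2% makes this frequent, and the cause there is sparse events rather than the covariates.

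Three further replies stand in part:

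- The 0.15 threshold belongs to 6.4.3.1, and *marked* may mean something stricter, so the 50–65% applies only if that rule is carried over.
- The 22% is an intravenous rate and this trial has no intravenous arm, so a small event count is an inference from other studies.
- Adjusting for a prognostic variable that is imbalanced by chance can reduce bias given that imbalance. The simulations assume unrelated covariates and cannot show that benefit. The fault is in selecting covariates by observed imbalance, not in adjustment as such.

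**Conclusion.** The point holds as a defect of specification in a secondary safety analysis. The rule for adding an adjusted result is data-driven and undefined, differs from the primary-analysis rule, and leaves precedence open. At the assumed rates the multi-covariate model would lack support: about 3 to 11 patients with events, and some coefficient non-estimable in roughly 20% to just over 80% of triggered fits. The loss specific to the treatment estimate is smaller, about 0–20% in three of the four scenarios and about 65% at 9% vs 2%, and a risk difference can still be calculated in all of these cases. The planned chi-square test is itself often outside its usual range.

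These sizes rest on 49 patients in total, 1:1 allocation, a logistic model, the 0.15 trigger carried over to safety, and event rates that the plan does not state. At 30–40% on fentanyl with one covariate the sparse-data problem largely goes away (9% of fits without a finite solution at 30% vs 10%, 0.4% at 40% vs 20%). The objection to the selection rule does not depend on the event rate.

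**What to change.** In 6.4.3.3, delete the conditional regression sentence. State that the main side-effect comparison is the unadjusted risk difference with a 95% confidence interval suited to sparse data (for example Newcombe), together with an exact test, whatever baseline balance is observed. State also that the 0.15 trigger in 6.4.3.1 does not apply to safety.

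If an adjusted estimate is wanted, name in advance one prognostic covariate that is already collected, for example nausea or vomiting before dosing. Fit it with a penalised (Firth) logistic model and label it a sensitivity analysis.

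The cost is a few sentences of analysis text, with no new data and no more patients. The downside is that the safety comparison can no longer be adjusted after the fact for a chance imbalance.
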